## **Race and Ethnicity**

In this study, collection of demographic information includes race and ethnicity. The scientific rationale is based on the need to assess variable response in safety and/or efficacy based on race or ethnicity.

## 4.3. Justification for Dose

The IP used in this Phase 3 study will be in insulin units delivered via prefilled pens using the dosing algorithm provided in Section 6.1. The dosing guidance for starting doses and dose titrations of LY3209590 is derived based on findings from Phase 2 studies and model-based simulations. These data informed dosing increments designed to balance the goal of achieving a balanced FBG target range and minimize occurrence of hypoglycemia.

## Justification for the LY3209590 single loading dose

Following a once-weekly subcutaneous administration of LY3209590, the time to reach steadystate PK without a loading dose is estimated to be between 8 and 10 weeks based on the long half-life of LY3209590. With a loading dose, the estimated time to reach steady state is within 2-3-weeks. Participants randomly assigned to LY3209590 with median FBG >120 mg/dL (6.6 mmol/L) will receive a single loading dose of LY3209590 that is 3-times the weekly dose calculated from their previous daily basal insulin dose multiplied by 7 (see Section 6.1). This strategy was designed to minimize loss of glycemic control when transitioning from the shorter duration once-daily basal insulins to a weekly insulin. This approach is supported by findings in the multiple-ascending dose Study BDCB, the Phase 2 Study BDCM, and model-based simulations.

For participants who are entering the study in good glycemic control

(FBG  $\leq 120 \text{ mg/dL}$  [6.6 mmol/L]), a loading dose is not recommended. In such cases, treatment should be started using the weekly dose calculated from their previous daily basal insulin dose multiplied by 7 (see Section 6.1).

Directions for conversion of the prior daily basal insulin dose to the LY3209590 weekly dose are described in Section 6.1. The method to calculate the one-time loading dose and the titration rules to be used beginning at Visit 5 (Week 2) are also described in Section 6.1.

## Justification for the insulin degludec starting dose

The starting dose for insulin degludec (U100) is the same as the daily dose of basal insulin the participant was taking prior to Visit 3 (Week 0). Insulin degludec will be titrated to achieve FBG target of 80-120 mg/dL (4.4-6.6 mmol/L) using an algorithm that is patterned after the well-established Riddle algorithm and other published algorithms (Meneghini et al. 2007, Kadowaki et al. 2017) but modified to balance efficacy and hypoglycemia for the same FBG targets as LY3209590 (Section 6.1).

Safety of study participants will be closely monitored during the early stages of dose titration to determine whether adjustments to the dose are needed to safely achieve FBG targets of 80-120 mg/dL (4.4-6.6 mmol/L) and will continue throughout the study (See Section 6.1).

# 4.4. End of Study Definition

The end of the study is defined as the date of last scheduled procedure shown in the SoA for the last participant in the trial.

A participant is considered to have completed the study if the participant has completed all periods of the study including the last scheduled procedure shown in the SoA.

# 5. Study Population

Prospective approval of protocol deviations to recruitment and enrollment criteria, also known as protocol waivers or exemptions, is not permitted.

## 5.1. Inclusion Criteria

Participants are eligible to be included in the study only if all the following criteria apply:

## Age

1. Are at least 18 years of age at screening (or older per local regulations)

## Type of Participant and Disease Characteristics

- 2. Have a diagnosis of T2D according to the WHO criteria currently treated with basal insulin
- 3. Are receiving  $\geq 10$  units of basal insulin per day and  $\leq 110$  units/day at screening
- 4. Have HbA1c value 6.5%-10% inclusive, as determined by central laboratory at screening
- 5. Have been treated with a stable regimen in the opinion of the investigator of one of the following insulin regimens (includes biosimilars) used according to local product label with or without non-insulin diabetes therapy for at least 90 days prior to screening:
  - once-daily U100 or U200 insulin degludec
  - once-daily U100 or U300 insulin glargine
  - once or twice-daily U100 insulin detemir (Levemir [Novo Nordisk A/S., Bagsvaerd, Denmark]), or
  - once or twice-daily human insulin NPH.

Acceptable non-insulin diabetes therapies may include 0 to up to 3 of the following:

- dipeptidyl peptidase (DPP-4) IV inhibitors
- SGLT2 inhibitors
- metformin
- alpha-glucosidase inhibitors, or
- GLP-1 receptor agonists.

**Note:** All non-insulin diabetes therapies must be used in accordance with the corresponding local product label at the time of screening, and participants should be willing to continue stable dosing throughout the study according to the protocol.

## Weight

6. Have a body mass index less than or equal to  $45 \text{ kg/m}^2$ , at screening

## **Participant Protocol Compliance**

- 7. Have a usual wake/sleep pattern such that midnight to 0600 hours will reliably reflect a usual sleeping period
- 8. In the investigator's opinion, are well-motivated, capable, and willing to
  - reliably take study-provided insulin injections as directed and other diabetes medications as required for this protocol.

- visually impaired persons who are not able to perform the injections must have the assistance of a sighted individual trained to inject the IP
- persons with physical limitations who are not able to perform the injections must have the assistance of an individual trained to inject the IP
- maintain an electronic study diary and use only the glucometer supplied for use in the study, including recording information on insulin doses and hypoglycemia events in the e-diary as required for this protocol
- wear the blinded continuous glucose-monitoring device supplied for use in this study at the specified times during the study and maintain proximity within 20 feet of the CGM receiver as required in the SoA and Section 8.1.5.2. Note: Participants who are already using CGM or FGM at study entry will be allowed to continue to use their personal CGM/FGM during the study when not wearing the study CGM. Participants must use the study-provided glucometer for all FBG values and any other BG values reported during the study
- not wear a personal CGM/FGM during the study blinded CGM assessments
- not initiate the use of personal CGM/FGM if not already routinely using CGM/FGM at study entry.

## Sex and Contraceptive/Barrier Requirements

Contraceptive use by participants should be consistent with local regulations regarding the methods of contraception for those participating in clinical studies.

- 9. Male participants: No male contraception required except in compliance with specific local government study requirements. See the requirements in Section 10.4, Appendix 4.
- 10. Female participants: See the requirements in Section 10.4, Appendix 4.

## **Informed Consent**

11. Capable of giving signed informed consent as described in Section 10.1, Appendix 1, which includes compliance with the requirements and restrictions listed in the ICF and in this protocol

## 5.2. Exclusion Criteria

Participants are excluded from the study if any of the following criteria applies:

## **Medical Conditions**

- 12. Have had a significant weight gain or loss in the past 3 months in the investigator's opinion (for example,  $\geq 5\%$ )
- 13. Have a diagnosis of T1D, latent autoimmune diabetes, or specific type of diabetes other than T2D (for example, monogenic diabetes, diseases of the exocrine pancreas, drug-induced or chemical-induced diabetes)
- 14. Are currently receiving or have received any time in the past 6 months, any of the following insulin therapies (outside of pregnancy) prior to screening, except for short-term treatment of acute conditions, and up to a maximum of 4 continuous weeks:
  - prandial insulin

- insulin mixtures
- inhaled insulin
- U-500 insulin, or
- continuous subcutaneous insulin infusion therapy

**Note:** Insulin use of any type or of any duration during a previous pregnancy is not considered an exclusion criterion.

- 15. Have received any of the following nonallowed diabetes medications within 90 days prior to screening: glinides, sulfonylureas, pramlintide, or thiazolidinediones
- 16. Have a history of greater than 1 episode of ketoacidosis or hyperosmolar state/coma requiring hospitalization in the 6 months prior to screening

## **Prior/Concomitant Therapy**

17. Are receiving chronic (>14 days) systemic glucocorticoid therapy (excluding replacement therapy for adrenal insufficiency; topical, intraocular, intranasal, or inhaled preparations or intra-articular injection) or have received such therapy for >14 days within the month preceding screening

## **Prior/Concurrent Clinical Study Experience**

- 18. Are currently enrolled in any other clinical study involving an IP or any other type of medical research, judged not to be scientifically or medically compatible with this study
- 19. Have participated, within the last 30 days in a clinical trial involving an IP. If the previous IP has a long half-life, 3 months or 5 half-lives (whichever is longer) should have passed prior to Visit 1 (Week -3)
- 20. Have previously completed or withdrawn from this study after having signed the ICF or any other study investigating LY3209590 after receiving at least 1 dose of the study basal insulin
- 21. Are investigator site personnel directly affiliated with this study and/or their immediate families. Immediate family is defined as a spouse, parent, child, or sibling, whether biological or legally adopted
- 22. Are Eli Lilly and Company employees or are employees of any third party involved in the study who require exclusion of their employees.

## **Diagnostic Assessments**

- 23. Cardiovascular: have had New York Heart Association Class IV heart failure or any of the following CV conditions in the past 3 months prior to screening:
  - acute myocardial infarction,
  - cerebrovascular accident (stroke), or
  - coronary bypass surgery.
- 24. Gastrointestinal: have undergone gastric bypass (bariatric) surgery, restrictive bariatric surgery (for example, Lap-Band®), or sleeve gastrectomy within 1 year prior to screening
- 25. Hepatic: have acute or chronic hepatitis, cirrhosis, or obvious clinical signs or symptoms of any other liver disease, except NAFLD (that is, study participants with NAFLD are eligible for participation), and/or

- have elevated liver enzyme measurements, as determined by the central laboratory at screening and as indicated below:
  - total bilirubin >2x the ULN (except for participants with Gilbert's syndrome)
  - ALT/serum glutamic pyruvic transaminase >3x ULN
  - AST/serum glutamic oxaloacetic transaminase >3x ULN, or
  - $\circ$  ALP >2.5x ULN
- 26. Renal: have a history of renal transplantation, are currently receiving renal dialysis, or have an eGFR <20 mL/min/1.73 m^2, calculated by the CKD-EPI equation, as determined by the central laboratory at screening
- 27. Have active or untreated malignancy, have been in remission from clinically significant malignancy (other than basal cell or squamous cell skin cancer) for less than 5 years, or are at increased risk for developing cancer or a recurrence of cancer in the opinion of the investigator
- 28. Have known hypersensitivity or allergy to any of the study medications or their excipients
- 29. Have any other serious disease or condition (for example, known drug or alcohol abuse or psychiatric disorder) that, in the opinion of the investigator, would pose a significant risk to the study participant, preclude the study participant from following and completing the protocol
- 30. Have evidence of a current or recent, within 6 months' time frame, history of any substance use disorder(s) of any severity as defined by the Diagnostic and Statistical Manual of Mental Disorders-5 (DSM-5) in the opinion of the investigator, except disorders of nicotine or caffeine use
- 31. Hematologic: have had a blood transfusion or severe blood loss within 90 days prior to Visit 1 (Week -3) or have known hemoglobinopathy, hemolytic anemia or sickle cell anemia, or any other traits of hemoglobin abnormalities known to interfere with the measurement of HbA1c in the opinion of the investigator
- 32. Women of childbearing potential (for example, not surgically sterilized and between menarche and 1-year postmenopausal) who
  - are pregnant or intend to become pregnant during the study
  - are lactating/breastfeeding (including the use of a breast pump)
  - are unwilling to remain abstinent or use birth control, and
  - test positive for pregnancy at the time of screening (Visit 1 [Week -3] or any time before randomization).

**Note:** a urine pregnancy test is conducted at Visit 3 (Week 0), and randomization will not be allowed with a positive result.

## 5.3. Lifestyle Considerations

Per the SoA (Section 1.3), qualified site staff will provide diabetes management counseling, which will include instructions on diet and exercise and education about the signs, symptoms, and treatment of hypoglycemia, should it occur. Study participants should continue their usual

exercise habits and generally follow a healthy meal plan throughout the course of the study. Diabetes self-management counseling may be reviewed throughout the study, as needed.

Study participants should not initiate an intensive diet/exercise program with the intent of reducing body weight at any time during the study, other than the lifestyle and dietary measures for diabetes treatment.

Study participants should be instructed not to donate blood or blood products during the study or for 4 weeks following the study.

# 5.4. Screen Failures

A screen failure occurs when a participant who consents to participate in the clinical study is not subsequently randomly assigned to study intervention. A minimal set of screen failure information is required to ensure transparent reporting of screen failure participants to meet the Consolidated Standards of Reporting Trials (CONSORT) publishing requirements and to respond to queries from regulatory authorities. Minimal information includes demography, screen failure details, eligibility criteria, and any SAE.

Individuals who do not meet the criteria for participation in this study (screen failure) will not be rescreened.

# 5.5. Criteria for Temporarily Delaying Enrollment of a Participant

This section is not applicable for this study. All entry criteria must be met within the specified intervals in the SoA.

# 6. Study Intervention(s) and Concomitant Therapy

Study intervention is defined as any investigational intervention(s), marketed product(s), placebo, or medical device(s) intended to be administered to/used by a study participant according to the study protocol.

Investigators and other study team members are expected to treat participants according to the nationally established standards of care for diabetes management in respective participating countries, except where that treatment would be in conflict with the protocol-provided treatment requirements. If there are no local/national standards of care for diabetes, the investigators should follow current published standards of care from the American Diabetes Association (ADA 2021).

## Site Responsibilities Related to Study Drugs

The investigator or their designee is responsible for the following:

- explaining the correct use and storage of the study drug to the participant and verifying those instructions are followed properly
- using the dosing algorithm to assess and titrate the doses weekly for the first 12 weeks and at least monthly throughout the remainder of the study
- maintaining accurate records of IP dispensing, and
- collecting of all unused study medication at the end of the study, returning it to Lilly, or designee, unless the sponsor and sites have agreed all unused medication is to be destroyed by the site, as allowed by local law.

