### **Data Monitoring Committee: Yes**

### 1.2. Schema

# **1.3.** Schedule of Activities (SoA)

The SoA described below should be followed for all participants enrolled in Study BDCU. However, for those participants whose participation in this study is affected by exceptional circumstances, such as pandemics or natural disasters, please refer to Section 10.7 for additional guidance.

	For procedures at the Screening/Lead In Period I (V1-V2) and Treatment Period II (V3-V22)																			
For	proced	ures a	nt Visi	it 23 1	to Vis	it 37,	ET, I	U V, 8	01 an	d 802	(Stud	ly Peri	od III)	) Safet	y F/u	Period	l, pleas	se see S	ection	1.3.2
Study Period I – Screenin	ng/Lea	d-In																	Comments	
Visit Number	1	2	3	4	5	6	7	8	9	10	11	12 13 14	15	16	17	18 19	20	21	22	
Weeks from Randomization	-3	-2	0	1	2	3	4	5	6	7	8	9 10 11	12	14	16	18 20	22	24	26	
Visit Interval Tolerance (days)		±3	_	±3	±3	±3	±3	±3	±3	±3	±3	±3	±3	±3	±3	±3	±3	±3	+3	
Fasting or Telehealth Visit			F			Т	F	Т	a	Т		Т	F	Т		Т		Т	F	T = telehealth visit; F = fasting visit; a see notes below
Informed consent	Х																			
Inclusion/exclusion criteria, review and confirm	X	х	X																	Review lab results and confirm I/E criteria
Demographics	Х																			
Preexisting conditions and medical history, including relevant surgical history	X																			
Prespecified medical history (indication and history of interest)	Х																			

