Fasting or Telehealth Visit			F			Т	F	Т	a	Т		Т	F	Т		Т		Т	F	T = telehealth visit; F = fasting visit; a see notes below
Insulin dose assessment/adjustment/ documentation			X	X	X	X	Х	X	X	X	Х	X	X	X	X	X	X	X	X	
IWRS	Х	Х	Х	Х	Х	Х	Х	Х	Х	Х	Х	Х	Х	Х	Х	Х	Х	Х	Х	
Dispense study intervention and related supplies			Х				Х						X						X	
Site administers study intervention and trains participant			Х																	
Observe patient administer LY3209590 study intervention				Х																Dose documented in e- diary immediately
Assess study intervention and storage compliance				Х	Х	Х	Х	Х	Х	Х	X	X	Х	X	Х	X	X	X	X	
Participant returns unused study drug							Х						Х						Х	

1.3.2. SoA for the T	reatm	ent F															
	Forn	rood								.	ĺ.	·	F/u Perio V3-V22)		,	ion 1 2	1
	ror p	roceu		Scree	ning	Perio	u I (v	1-12)	anu 1	reatm	ent Pe	riou II (	v 3- v 22	, piease		1011 1.3.	1
					Stu	ıdy Po	eriod	II - Tr	eatme	nt Per	iod				Perio	udy od III ty F/u	Comments
Visit Number	23 24	25	26 27	28	29	30	31	32	33 34	35	36	37	ET	UV	801	802	
Weeks from Randomization	28 32	36	40 44	48	50	52	60	64	68 72	74	76	78			80	83	
Visit Interval Tolerance (days)	±7	±7	±7	±3	±7	±3	±7	±7	±7	±3	±7	$\pm 3$			+7	±7	
Fasting or Telehealth Visit	Т	F	Т	a	Т	F	Т	F	Т	a	Т	F	F		Т	F	T = telehealth visit; F = fasting visit; a see below notes
Concomitant medications	Х	Х	Х	Х	Х	Х	Х	Х	Х	Х	Х	Х	Х	Х	Х	Х	
Adverse events (AEs)	Х	Х	Х	Х	Х	Х	Х	Х	Х	Х	Х	Х	Х	Х	Х	Х	See Section 10.3
Physical Evaluation	•	•	1	1		ī	1	1	•	1					1	1	
Weight		Х		Х		Х		Х		Х		Х	Х			Х	See Section 5.3
Vital signs		Х		х		Х		Х		Х		Х	Х			Х	See Section 8.2.2
Physical examination												Х	Х			Х	Additional physical examinations may be completed as necessary at PI discretion
Hypoglycemia events	Х	Х	Х	Х	Х	Х	Х	Х	Х	Х	Х	Х	Х	Х	Х	Х	
12-lead ECG (local)												Х	Х				See Section 8.2.3

			F	For Tr	eatm	ent Po	eriod (	(V23-V	/37), F	ET, UV	/, and	Safety F	F/u Perio	d (801-8	02)		
	For p	roced	ures at	Scree	ning ]	Perio	d I (V	1-V2)	and T	reatm	ent Pe	riod II (	V3-V22 )	, please	see Sect	ion 1.3.	1
					Stu	ıdy Po	eriod	II - Tr	eatme	nt Per	iod				Peri	udy od III ty F/u	Comments
Visit Number	23 24	25	26 27	28	29	30	31	32	33 34	35	36	37	ET	UV	801	802	
Weeks from Randomization	28 32	36	40 44	48	50	52	60	64	68 72	74	76	78			80	83	
Visit Interval Tolerance (days)	±7	±7	±7	±3	±7	±3	±7	±7	±7	±3	±7	±3			+7	±7	

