Patient-Reported Outcomes	(Elect	ronic)		-	-	-						-		-		-	
Diabetes Treatment Satisfaction Questionnaire - Change						Х						Х					
EQ-5D-5L						Х						Х	Х				
Simplicity Questionnaire – Study Drug (SIM-Q)													Х				Administered only if ET occurs before Visit 26
Basal Insulin Experience: Preference												Х	Х				
Basal Insulin Experience: Likelihood of Incorporating into Routine												Х	Х				
Laboratory Tests and Samp	le Coll	ection	s														
Hematology						Х						Х	Х			Х	
Hemoglobin A1c (HbA1c)		Х				Х		Х				Х	Х			Х	

	For n	roced						`				•		d (801-8), please		ion 1.3.	1
								 						, preude s	Stu Perio	udy od III ty F/u	Comments
Visit Number	23 24	25	26 27	28	29	30	31	32	33 34	35	36	37	ET	UV	801	802	
Weeks from Randomization	28 32	36	40 44	48	50	52	60	64	68 72	74	76	78			80	83	
Visit Interval Tolerance (days)	±7	±7	±7	±3	±7	±3	±7	±7	±7	±3	±7	±3			+7	±7	
Fasting or Telehealth Visit	Т	F	Т	a	Т	F	Т	F	Т	a	Т	F	F		Т	F	T = telehealth visit; F = fasting visit; a see below notes
Clinical chemistry						Х						Х	Х			Х	
Glucose		Х						Х									
Lipid panel						Х						Х	Х			Х	
Urinalysis												Х	Х			Х	
Urine pregnancy													Х			Х	Additional pregnancy testing may be performed as necessary or if required by local regulations
C-Peptide												Х	Х				
eGFR (CKD-EPI)						Х						Х	Х			Х	
UACR						Х						Х	Х			Х	
Pharmacokinetic (PK) samples						Х						Х	Х			Х	All randomized participants

			F	for Tr	eatm	ent Po	eriod (	(V23-V	/37), I	ET, UV	, and	Safety I	F/u Perio	d (801-8	02)		
	For p	roced	ures at	Scree	ning	Perio	d I (V	1-V2)	and T	reatm	ent Pe	riod II (	V3-V22 )	, please	see Sect	ion 1.3.	1
					Stu	ıdy Po	eriod	II - Tr	-	nt Per	iod				Perio	ıdy od III ty F/u	Comments
Visit Number	23 24	25	26 27	28	29	30	31	32	33 34	35	36	37	ET	UV	801	802	
Weeks from Randomization	28 32	36	40 44	48	50	52	60	64	68 72	74	76	78			80	83	
Visit Interval Tolerance (days)	±7	±7	±7	±3	±7	±3	±7	±7	±7	±3	±7	±3	_		+7	±7	
Fasting or Telehealth Visit	Т	F	Т	a	Т	F	Т	F	Т	a	Т	F	F		Т	F	T = telehealth visit; F = fasting visit; a see below notes
Immunogenicity (ADA) samples						Х						Х	Х			Х	All randomized participants.
Stored Samples																	
Exploratory biomarker samples												Х	Х				
Randomization and Dosing																	
Insulin dose assessment /adjustment/documentation	Х	Х	Х	Х	Х	Х	Х	Х	Х	Х	X	Х	Х	Х			See Section 6.5.

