## **Insulin Dose Titration and Dose Maintenance**

In this treat-to-target study, both treatment groups will undergo titration to achieve and maintain an FBG target within the range of 80-120 mg/dL (4.4-6.6 mmol/L). Active titration will occur in both treatment groups between Visits 3 to 15 (Weeks 0 to 12) which will be designated as the Titration Period with the goal to achieve insulin dose stabilization by Visit 15 (Week 12) with a minimum of monthly adjustments as necessary during the Maintenance Period from Visit 15 to 37 (Weeks 12 to 78).

Using the e-diary-linked study-provided glucometer, participants in both treatment groups will perform daily self-monitored FBGs. A minimum of 3 FBG readings on separate days each week must be obtained so that investigators can review the data to make dose adjustments using the titration algorithms for once-weekly or once-daily insulins (Sections 6.1.4 and 6.1.5). The median FBG to use in determining the dose adjustments starting at Visit 5 (Week 2) is obtained from the 3 most recent FBGs in the previous week. The median is the middle value when the 3 values are placed in ascending or descending order. For example, if a participant's FBGs for the past 3 consecutive measurements were 180, 202, and 190, the median is 190.

**Note:** If the participant has only 2 FBG readings for the week, then the lesser of the readings should be used to determine the dose adjustments. If only 1 FBG measurement is available, determination if dose is changed using only a single FBG value is at the discretion of the investigator.

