## 6.8.5. Treatment after the End of the Study

## 6.8.5.1. Treatment after Study Completion

Study interventions will not be made available to study participants after Visit 37 (Week 78) or after the participant's early discontinuation from study treatment.

At the last treatment visit (Visit 37 [Week 78] or ET visit), the investigator will prescribe a nonstudy basal insulin for use during the safety follow up period. Participants will continue their concomitant non-insulin antihyperglycemic medications at the discretion of the investigator and continue to monitor their FBG and complete the e-diary.

**Study Participants treated with LY3209590:** Study participants will receive the last injection of LY3209590 at Week 77 of the study and can begin the transition to the non-study insulin after Visit 37 (Week 78). At Visit 37 (Week 78), the investigator will review the instructions for transitioning to the non-study insulin. During this transition period, the participant's FBG should be used to guide dose initiation and adjustment for the insulin prescribed for the safety follow-up period.

No daily basal insulin will be required until the FBG is above 120 mg/dL (6.6 mmol/L) for 2 consecutive measurements. The prescribed non-study daily basal insulin should be started at a dose of 10 units/day and adjusted during the safety follow-up period based on FBG and according to the modified Riddle algorithm or investigator judgement in accordance with any country-specific label. Dose adjustments made for the non-study insulin during the safety follow-up period should be documented in the eCRF. An unscheduled visit in addition to Visit 801 may occur during this time to facilitate the transition to the non-study daily basal insulin.

Since LY3209590 has a half-life of approximately 17 days, a careful titration of the daily basal insulin is necessary to prevent hypoglycemia due to overlapping insulin action. Therefore, the investigator should consider titrating the daily insulin to reach 50% of the required daily dose at approximately 2-weeks and 80% at approximately 4-weeks.

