## 8.1.5.5. Investigator Portal

Participant e-diary information including insulin dosing data, SMBG values, and events of hypoglycemia will be available for review through a web-based portal that can be accessed by designated investigative site personnel at any time. The site personnel can remotely view the completed e-diary data at any time during the study including between visits and print reports of diary data.

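### The protocol requires dose assessment at least monthly to Week 78, but the Schedule of Activities has none between Week 52 and Week 60; one remote check near Week 56 in both arms would close that gap.

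*Protocol*

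**What the plan says.** Protocol Section 6 (Site Responsibilities Related to Study Drugs) makes the investigator or designee responsible for algorithm-based assessment and titration of both insulins, at this frequency: "weekly for the first 12 weeks and at least monthly throughout the remainder of the study". Section 6.1.3 (Insulin Dose Titration and Dose Maintenance) sets the same floor, with Week 12 as the target for a stable dose: "with a minimum of monthly adjustments as necessary during the Maintenance Period from Visit 15 to 37 (Weeks 12 to 78".

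The opening of Section 1.3 states: "The SoA described below should be followed for all participants enrolled in Study BDCU". Section 8 also treats adherence to the SoA as mandatory.

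The visit weeks in the Section 1.3.2 table begin "Weeks from Randomization 28 32 36 40 44 48 50 52 60 64". The row "Insulin dose assessment /adjustment/documentation" is marked at every treatment visit from Visit 23 to Visit 37, and also under early termination and unscheduled visits. The diary compliance row, which covers fasting glucose, hypoglycemia and dose, follows the same pattern at the treatment visits. Visit 30 is Week 52 and Visit 31 is Week 60. The visit numbers are consecutive, so no column was lost in reading the table.

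Section 8.1.5.5 (Investigator Portal) adds: "The site personnel can remotely view the completed e-diary data at any time during the study including between visits". The SoA notes allow unscheduled visits at any time.

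**The concern.** The text sets a monthly floor and the SoA leaves eight weeks without a scheduled dose assessment. A site that works from the SoA alone misses the protocol's own minimum. A site that works from Section 6 has to arrange the missing assessment itself.

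What is at stake is safety monitoring and consistent titration. Section 2.3.1 provides automated alerts for potential severe hypoglycemia. The alerts it describes do not cover non-severe lows, including readings below 54 mg/dL, or persistently high fasting glucose. The titration rules in Sections 6.1.4 and 6.1.5 look back one week only, so the Week 60 assessment would not act on about seven of the preceding eight weeks. In a 4-week interval that figure is about three. After Week 26 the rescue criterion in Section 6.8.1 is a 2-week average fasting glucose above 200 mg/dL, and such an episode could begin and end inside the gap without scheduled review.

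The point weighs more for LY3209590. About eight weekly doses fall in the gap, and Section 6.8.5.1 notes "Since LY3209590 has a half-life of approximately 17 days", so an unsuitable dose is slow to wear off once noticed. The gap also lies inside the 0 to 78 week window of the key secondary nocturnal hypoglycemia rate.

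**Working it through.** **Inputs.** Required frequency: at least monthly from Week 12 to Week 78 (Protocol Sections 6 and 6.1.3). Visit weeks and windows: Protocol Sections 1.3.1 and 1.3.2. Half-life of LY3209590: about 17 days (Section 6.8.5.1). I take a month as 28 to 31 days.

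**Maintenance visits.** Weeks 12, 14, 16, 18, 20, 22, 24, 26, 28, 32, 36, 40, 44, 48, 50, 52, 60, 64, 68, 72, 74, 76 and 78. That is 23 visits and 22 intervals.

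**Nominal interval = difference in visit weeks.**

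- 2 weeks: 8 (Weeks 12 to 28) + 2 (Weeks 48 to 52) + 3 (Weeks 72 to 78) = 13
- 4 weeks: 5 (Weeks 28 to 48) + 3 (Weeks 60 to 72) = 8
- 8 weeks: 1 (Weeks 52 to 60)
- Check: 13 × 2 + 8 × 4 + 1 × 8 = 26 + 32 + 8 = 66 weeks = 78 − 12

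**The Week 52 to 60 interval.**

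- Nominal: 8 × 7 = 56 days
- With windows of ±3 and ±7 days: 56 − 10 = 46 to 56 + 10 = 66 days
- Share of the maintenance period: 8/66 = 12%
- Share of the separate 52 to 78 week hypoglycemia period in SAP Section 4.6.3.1.1: 8/26 = 31%
- In LY3209590 half-lives: 56/17 = 3.3

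Even the shortest in-window length, 46 days, exceeds 31 days. No other nominal interval does.

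**With a contact at Week 56, window assumed ±7 days.**

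- Weeks 52 to 56: 28 ± (3 + 7) = 18 to 38 days
- Weeks 56 to 60: 28 ± (7 + 7) = 14 to 42 days
- Longest nominal maintenance interval: falls from 56 to 28 days

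For comparison, an existing 4-week interval with ±7-day windows at both ends (for example Weeks 28 to 32, or 60 to 64) already ranges over 28 ± 14 = 14 to 42 days. The new intervals are no wider.

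**The case against.** The strongest reply is that a floor on dose assessment and a grid of visits do not conflict. Section 6 does not say the monthly assessment must happen at a scheduled visit, and Section 6.1.3 asks for adjustments only as needed. The means are in place: the unscheduled-visit column carries a dose-assessment mark, and the portal shows doses, glucose and hypoglycemia between visits. Participants supply at least three fasting readings a week. On this view only a prompt is missing.

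It stands that a site can comply and that the Section 6 duty exists whatever the SoA shows. But the SoA otherwise carries out that duty, with weekly visits to Week 12 and nominal intervals of 4 weeks or less afterwards, and the documents give no reason for the single exception. The as-needed wording in Section 6.1.3 applies to adjustments. Section 6 requires the assessment, without which need cannot be judged.

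It also stands that visit windows stretch 4-week intervals to 42 days, with or without the added contact, so the fix restores the monthly rule at nominal timing only.

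The remaining points limit the size of the concern. No figure is available for how many participants would need a dose change in Weeks 52 to 60. Doses are meant to be stable by Week 12, and participants are trained to treat lows. The 3.3 half-lives describe how slowly an unsuitable dose clears, not how likely a dose is to become unsuitable. Six further scheduled assessments (Weeks 60, 64, 68, 72, 74 and 76) precede the Week 78 HbA1c. Being inside the key secondary window is a matter of location; no effect on the rate ratio has been shown.

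**Conclusion.** The concern holds. The SoA fails the protocol's own monthly rule at one place, Weeks 52 to 60, by a margin that the visit windows cannot absorb: 46 days at the shortest, 56 nominal, 66 at the longest.

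The consequence is modest. It is a missing prompt for reviewing non-severe lows and high fasting glucose over 12% of the maintenance period. The gap is identical in both arms and begins 26 weeks after the primary endpoint, so the primary analysis and the sample size are unaffected and no between-arm bias is claimed. The conclusion rests on reading monthly as 28 to 31 days and on the visit weeks and windows as printed. The clinical yield of an added check cannot be estimated from the documents. The change should be made because it is cheap and brings the schedule into line with the text.

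**What to change.** Add one remote dose assessment at Week 56 (±7 days) to the Section 1.3.2 table for both arms. It can be a telehealth contact like those at Weeks 28, 32, 40 and 44, or a scheduled e-diary portal review. Mark the dose assessment, hypoglycemia events and diary compliance rows for it. Leave the dosing algorithms and their one-week look-back unchanged.

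The cost is one SoA column and one remote check for each participant still on treatment at Week 56, at most 939. No site visit, sample, device or drug dispensing is needed. The downside is a small added burden on sites and participants.
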